Immune Related Response Criteria: Tumor response will be assessed by using immune-related response criteria (irRC). The imaging service provider (core laboratory) will acquire images from clinical sites. Review of image data will be conducted in the core lab by qualified and trained radiologists blinded to treatment status. The procedures used for CT/MRI image analysis, reporting of tumor response data and storage and archiving of images will follow the standards laid out in the prospectively determined Imaging Review Charter.

irRC Evaluation:

The detailed evaluation methodology is documented in the Imaging Review Charter. Briefly, for each imaging session, the sum of the products of the two largest perpendicular diameters (SPD) of all index lesions (5 lesions per organ, up to 10 visceral and 5 cutaneous lesions with

a minimum size of $\geq 5 \times 5$ mm) will be calculated. Index lesions will be identified at baseline, and will be followed throughout the patient's participation in this study. At each subsequent imaging assessment, new lesions (defined as a lesion with $> 5 \times 5$ mm measurements) will have their products of diameters measured for use in calculating tumor burden. Tumor burden will be calculated by summing the SPD of target lesions with the SPD of the new measurable lesions.

Table 1: irRC Response Definitions:

Complete Response (irCR):	Disappearance of all lesions in two consecutive observations not less than 4 weeks apart
Partial Response (irPR):	$\geq 50\%$ decrease in tumor burden compared with baseline in two observations at least 4 weeks apart
Stable Disease (irSD):	50% decrease in tumor burden compared with baseline cannot be established nor 25% increase compared with nadir
Progressive Disease (irPD):	At least 25% increase in tumor burden compared with nadir (at any single time point) in two consecutive observations at least 4 weeks apart
Not Evaluable (NE)	Progression has not been documented and one or more index lesions have not been assessed or have been assessed using a different method than baseline that makes comparability impossible.

Table 2: Derivation of irRC Overall Response

Overall lesions response at each assessment			
Index and new lesions (tumor burden), * %	Non-Target Lesions	New Lesions	Overall Response
$\downarrow 100$	Absent	Absent	irCR †
$\downarrow 100$	Stable	Any	irPR †
$\downarrow 100$	Unequivocal progression	Any	irPR †
$\downarrow > 50$	Absent/Stable	Any	irPR †

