$\downarrow > 50$	Unequivocal progression	Any	irPR †
$\downarrow < 50$ to $< 25\uparrow$	Absent/Stable	Any	irSD
$\downarrow < 50$ to $< 25\uparrow$	Unequivocal progression	Any	irSD
> 25	Any	Any	irPD †

* Decreases assessed relative to baseline, including measurable lesions only ($\geq 5 \times 5$ mm).

† Assuming response (irCR and irPR) and progression (irPD) are confirmed by a second, consecutive assessment at least 4 weeks apart.

Best overall response (BOR), determined from the sequence of cycle responses assessed, will be used for analyzing ORR and DCR.

Progression Free Survival (PFS): This will be defined as time from randomization to progression of disease or death as defined in Table 1 below, whichever is earlier. Patients surviving without objective disease progression at the end of the data inclusion cutoff date will be censored. If there is no baseline disease progression assessment, then PFS will be censored at randomization. An adequate tumor assessment is defined as a set of radiologic images, which has been transmitted to the central imaging vendor for the purposes of assessing change in tumor measurements according to the immune related response criteria. In order to be considered adequate, the images should include assessment of chest, abdomen and pelvis using the same imaging modality as the baseline scan and should include all target and non-target lesions.

Table 3: Definitions for Assessment of PFS

Situation	Date of Progression or Censoring	Outcome
No baseline assessment	Randomization	Censored
Progression documented between scheduled visits	Next scheduled visit	Progressed
No progression	Date of last visit with adequate assessment	Censored
Investigator claim of clinical progression	Scheduled visit (or next scheduled visit if between visits)	Progressed
Treatment discontinuation for toxicity or other reason	Date of last visit with adequate assessment	Censored
New anticancer treatment started with no claim of progression	Date of last visit with adequate assessment	Censored
Death before first PD assessment	Date of death	Progressed
Death between adequate assessment visits or after patient misses one assessment visit	Date of death	Progressed
Death after an extended lost-to-follow-up time (two or more missed assessments)	Last visit with adequate assessment	Censored

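### The SAP does not settle whether a first irPD with no confirming scan is a PFS event, and a literal reading can censor the patient at the scan that shows progression

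*SAP*

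**What the plan says.** **Definition of progression.** SAP 3.2 defines PFS as "time from randomization to progression of disease or death as defined in Table 1 below, whichever is earlier". Table 1 gives irPD as "At least 25% increase in tumor burden compared with nadir (at any single time point) in two consecutive observations at least 4 weeks apart". The Table 2 footnote repeats the condition: "Assuming response (irCR and irPR) and progression (irPD) are confirmed by a second, consecutive assessment at least 4 weeks apart".

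**Event and censoring rules.** These are in SAP Table 3.
- Counted as progressed: "Progression documented between scheduled visits"; "Investigator claim of clinical progression"; and "Death between adequate assessment visits or after patient misses one assessment visit".
- Censored at the last visit with an adequate assessment: patients with no progression; those under "Treatment discontinuation for toxicity or other reason"; and deaths after two or more missed assessments.

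**Other SAP and protocol statements on PFS.** SAP 3.2 adds: "Patients surviving without objective disease progression at the end of the data inclusion cutoff date will be censored". SAP 7.2 censors discontinued or lost patients who show no evidence of progression, and refers to Table 1 for how. Protocol 10.4 defines PFS by tumor progression or death and does not mention confirmation.

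**Who gets the confirming scan.** Protocol 5.4 (Cycle 6+ and Study Calendar footnote j) schedules it at 4 weeks +/- 3 days for patients who elect to continue therapy. Under the End of Study Visit, it waives repeat measurements for patients who stopped because of progressive disease. Protocol 7.5.1 requires a second scan unless the patient is deteriorating rapidly. Protocol 5.2 requires therapy to stop on irRC progression and does not say whether that means first or confirmed.

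**The concern.** PFS status depends on a second scan that the visit schedule does not ask for in patients who stop drug at the first irPD. If irPD must be confirmed, such a patient has not progressed by Table 1, and the Table 3 rows that remain censor at the last adequate assessment. That assessment is the scan that showed the growth.

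Censoring there is informative. Kaplan-Meier assumes that a censored patient has the same future risk as those still followed, yet these patients leave the risk set because their tumors grew. Two programmers could code the same patient differently, each with SAP text in support. PFS is a named secondary endpoint, tested at two-sided 0.05 (SAP 8.4.2).

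**Working it through.** **1. The cross-references.** Table 1 stands above the sentence that places it below. It does not define death and has no censoring rules. Table 3 stands below and has both. SAP 7.2 makes the same reference. Both evidently mean Table 3.

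**2. One patient under each reading.** The patient has a first irPD at a scheduled scan, stops drug, and has no later scan.

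| Step | Table 1 taken literally | Table 3 meant |
|---|---|---|
| Is a single scan progression? | No, two are needed | Table 3 sets no confirmation condition |
| Row that applies | No progression, or discontinuation for toxicity or other reason | None fits: the documented-progression row covers only findings between visits |
| Result | Censored at that scan, unless clinical progression is claimed or death comes before two missed assessments | Event, by inference |

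The sentences in SAP 3.2 and 7.2 that describe who is censored imply, by their converse, that this patient is an event. Neither says so, and objective progression could itself mean confirmed irPD.

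**3. Size.** The documents give no PFS median, event count or power, so there is no plan figure to reproduce.

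Inputs from the documents:
- 400:200 allocation and 18 months of follow-up
- control median OS of 4.6 months, used in both arms (no treatment effect)
- scans every 8 weeks: 56/30.4375 = 1.84 months

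Assumed inputs:
- exponential time to progression with median 2-3 months, independent of death
- 40-60% of patients stop at first irPD, equally by arm
- clinical progression is claimed for 0%, 50% or 80% of stoppers
- stoppers are not rescanned
- two missed assessments means 16 weeks, or 3.68 months

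In simulation, 311-358 of 600 patients have a first irPD while alive.

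Stoppers who die within 16 weeks, and so remain events: 1 - 0.5^(3.68/4.6) = 42.6%. The other 57.4% are censored at the progression scan. With no claims:
- low end: 311 x 0.40 x 0.574 = 71
- high end: 358 x 0.60 x 0.574 = 123

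Simulation gives 72-123.

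| Claims among stoppers | Censored at the progression scan | Share of PFS events counted | Median PFS, literal (months) |
|---|---|---|---|
| 0% | 72-123 | 79-88% | 2.4-3.3 |
| 50% | 36-61 | 90-94% | 1.8-2.7 |
| 80% | 14-25 | 96-98% | 1.8-2.3 |

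When the first irPD counts, the median is 1.8 months. The hazard ratio under literal coding is 1.00, with p<0.05 in 4-6% of trials. If half of the stoppers alive at 28 days are rescanned and confirmed, the median with no claims falls to 1.9-2.7 months.

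**4. Sensitivity of the comparator.** The 1.8 months is simply the first scan. PFS just after it is 0.5^(1.84/TTP) x 0.5^(1.84/OS), where TTP and OS are the two medians. With TTP 3 months:
- OS 4.6: 0.654 x 0.758 = 49.5%, so the median falls at that scan
- OS 6.0: 0.654 x 0.809 = 52.9%, so the median falls later, at about 2.3 months

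Wider assumptions (TTP 1.5-4 months, OS 4.6 or 6.0, 30-90% of first irPDs unconfirmed, no claims) give a median of 1.8-3.2 months when the first irPD counts. Literal coding with the death rows applied gives 1.8-4.6 months with 58-92% of patients as events. If the discontinuation row overrides the death rows, it gives 1.8-5.5 months with 37-86% as events.

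**5. The confirmation window.** 28 - 3 = 25, so the window allows a scan on days 25-27, which is less than 4 weeks after the first.

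**The case against.** The strongest reply is that this is a numbering slip. Read the references as Table 3, the table titled for PFS, and the confirmation requirement is no longer part of the PFS definition. SAP 7.2 already limits censoring to patients without evidence of progression, and calling a stop for progression an other reason is strained. Protocol 7.5.1 requires a second scan unless there is rapid deterioration, and patients who do deteriorate rapidly are natural candidates for a clinical-progression claim. The Imaging Review Charter, which was not supplied, may fix how the core laboratory reports an unconfirmed irPD.

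Much of this stands. The references do evidently mean Table 3, the surrounding text leans toward an event, and the scenario with no claims is an extreme. But correcting the references alone leaves Table 3 without a row for the case, and the confirmation condition stays in the irPD definition and the Table 2 footnote. Protocol 5.4 pulls against 7.5.1 for patients who stop. The charter may settle the reader's call, but the censoring rules are in the SAP.

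It can also be said that a patient off treatment has no scheduled scans and so misses none. Every later death would then be an event at its own date: fewer patients would be censored, but their events would still be dated later than the progression scan. The SAP does not say which applies.

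Finally, requiring confirmation in the primary PFS analysis is also defensible. That is a reason to report both rules.

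**Conclusion.** The concern holds as an ambiguity with conflicting implications. Followed literally, the SAP can censor a patient at the scan that shows progression, and nothing in Table 3 prevents it.

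A reader might infer more in three ways, none of which the documents support.
- **That the SAP explicitly contradicts itself.** The event reading is only implied, and the censoring reading depends on a mistaken table number.
- **That every unconfirmed first irPD is censored.** A clinical-progression claim, or death before two missed assessments, makes the patient an event.
- **That the treatment comparison is biased.** With equal stopping the simulated hazard ratio stays about 1.00. A hypothetical 60% versus 40% split, with more stopping on MABp1 and no claims, gives 0.88-0.91 across separate simulations, and about 0.98 at 80% claims. The trial is double blind with blinded central reads, and nothing in the documents suggests such a split.

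What remains is a possible lengthening of median PFS in both arms, from nothing to about 1.5 months (3.3 - 1.8) under the main assumptions. It depends on assumed rates of stopping, claims and rescanning, on the OS median, and on whether off-treatment patients count as missing assessments. Overall survival is unaffected. The plan should be changed; confidence in the size is moderate at best.

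**What to change.** In the SAP:
- In 3.2, refer to Table 3 for PFS and keep Table 1 for the irRC categories. In 7.2, change the reference to Table 3.
- Add two Table 3 rows: progression at a scheduled scan, and a first irPD with no later adequate scan. In both, the event date is the first scan with an increase of 25% or more over nadir, unless a later adequate scan contradicts it.
- Limit the row for discontinuation for toxicity or other reason to patients without evidence of radiographic progression, in line with 7.2. State which row takes precedence, and whether patients off treatment can miss assessments.
- Run the confirmed-only rule as a sensitivity analysis. Report by arm how many first irPDs had no confirming scan, and why.

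The protocol passages on stopping and confirmation (5.2, 5.4 including footnote j, and 7.5.1) must be reconciled with each other. So must the 4 weeks +/- 3 days window and the minimum of 4 weeks. No clinical rule is proposed here.

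**Cost.** SAP wording and one extra analysis, with no new scans. PFS may look shorter in both arms, and some pseudo-progressions among stoppers will count as events. If 5-20% of first irPDs are pseudo-progression, equally by arm (assumed), the proposed rule gives a hazard ratio of 1.00-1.03 at the 60/40 split and 0.97-0.99 at the reverse. A rate that differs by arm was not tested, which is a further reason to show both rules.

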Cycle 6+/- Follow up visits will occur every 14 days (+/- 2 days) for all subjects who remain on trial:

- Physical Exam
- Weight

- Vital Signs (pre-infusion)
- ECOG Evaluation
- Hematology panel: CBC with differential, platelets (pre-infusion)
- Chemistry panel and serum pregnancy (pre-infusion same tube). Serum pregnancy to be completed every 2 cycles.
- Urinalysis (pre-infusion)
- CRP (pre-infusion)
- PK Sampling (pre-infusion)
- Study Drug infusion
- Vital signs (60 minutes post-infusion)
- PK Sampling (30-90 minutes post-infusion)
- Adverse Event monitoring
- Concomitant Medications
- Tumor Measurements (every 8 weeks, i.e. within 7 days prior to C9D1, C13D1 etc.). Upon documentation of radiographic progression, confirmatory tumor measurements to be repeated at 4 weeks +/- 3 days only for patients who elect to continue on therapy until confirmation of progression. If this scan confirms progression, treatment is to be discontinued. If the confirmatory measurements indicate stable disease or better, the patient may elect to continue treatment with radiographic tumor assessments every 8 weeks from Day 1 of the current treatment cycle until progression.

End of Study Visit- This visit should be completed within 14 days for any subject who elects to come off trial or who comes off due to AEs, toxicities, or decline in performance status:

- Physical Exam
- Weight
- Vital Signs
- ECOG Evaluation
- Hematology panel: CBC with differential, platelets
- Chemistry panel
- Urinalysis
- CRP
- Adverse Event monitoring
- Serum Pregnancy
- PK Sampling
- EORTC QLQ-C30
- Concomitant Medications / Non-Drug Therapies review
- DEXA Scan--for any subject who completes visits at least through C3D1, but discontinues prior to C5D1
- Tumor Measurements--for subjects with clinical progression, every effort should be made to obtain radiographic restaging. If subjects are discontinued due to evidence of progressive disease, then tumor measurements do not need to be repeated.

Follow up for Overall Survival

Subjects, who come off trial for any reason after C1D1, will be contacted by phone after 30 days of the last dosing visit for adverse events and ECOG performance status, and at every 4-6 weeks

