^j Following Cycle 6 Day 1, tumor measurements are to be repeated every 8 weeks (within 7 days prior to C9D1, C13D1, C17D1, etc.). Upon documented progression, confirmatory tumor measurements are to be repeated at 4 weeks +/- 3 days, for patients who elect to continue therapy until confirmation of progression.

^k Tumor measurements should be performed, if possible, for subjects with clinical progression, to obtain radiographic restaging.

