The same method of assessment and the same technique should be used to characterize each identified and reported lesion at baseline and during follow-up. Imaging-based evaluation is preferred to evaluation by clinical examination when both methods have been used to assess the antitumor effect of a treatment.

Clinical lesions. Clinical lesions will only be considered measurable when they are superficial (e.g., skin nodules and palpable lymph nodes). In the case of skin lesions, documentation by color photography, including a ruler to estimate the size of the lesion, is recommended.

Helical (or Spiral) CT and MRI. These techniques should be performed with cuts of 5 mm or less in slice thickness contiguously. Spiral CT should be performed using a ≤ 5 mm contiguous reconstruction algorithm. This applies to tumors of the chest, abdomen, and pelvis. Head and neck tumors and those of extremities usually require specific protocols.

7.5.1 Immune Related Response Criteria:

Evaluation of Target Lesions

Evaluation of radiographic response will be conducted using the Immune Related Response Criteria (irRC), as described by Wolchok, et al⁶⁰. “For irRC, only index and measurable new lesions are taken into account. At the baseline tumor assessment, the sum of the products of the two largest perpendicular diameters (SPD) of all index lesions (five lesions per organ, up to 10 visceral lesions and five cutaneous index lesions) is calculated. At each subsequent tumor assessment, the SPD of the index lesions and of new, measurable lesions ($\geq 10 \times 10$ mm; up to 5 new lesions per organ: 5 new cutaneous lesions and 10 visceral lesions) are added together to provide the total tumor burden:”

$$\text{Tumor Burden} = \text{SPD}_{\text{index lesions}} + \text{SPD}_{\text{new, measurable lesions}}$$

Complete Response (irCR): irCR, complete disappearance of all lesions (whether measurable or not, and no new lesions). Confirmation by a repeat, consecutive assessment no less than 4 weeks from the date first documented.

Partial Response (irPR): irPR, decrease in tumor burden $\geq 50\%$ relative to baseline confirmed by a consecutive assessment at least 4 weeks after first documentation.

Progressive Disease (irPD): irPD, increase in tumor burden $\geq 25\%$ relative to nadir (minimum recorded tumor burden) confirmation by a repeat, consecutive assessment no less than 4 weeks from the date first documented.

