- If a patient is classified as having irPD at a post-baseline tumor assessment, then confirmation of irPD by a second scan in the absence of rapid clinical deterioration is required. The definition of confirmation of progression represents an increase in tumor burden $\geq 25\%$ compared with the nadir at two consecutive time points at least 4 weeks apart. **It is recommended that this be done at the discretion of the investigator because follow-up with observation alone may not be appropriate for patients with a rapid decline in performance status.**

Stable Disease (irSD): irSD, not meeting criteria for irCR or irPR, in absence of irPD.

Table 1. Comparison between WHO criteria and the irRC

	WHO	irRC
New, measurable lesions (i.e., $\geq 5 \times 5$ mm)	Always represent PD	Incorporated into tumor burden
New, nonmeasurable lesions (i.e., $< 5 \times 5$ mm)	Always represent PD	Do not define progression (but preclude irCR)
Non-index lesions	Changes contribute to defining BOR of CR, PR, SD, and PD	Contribute to defining irCR (complete disappearance required)
CR	Disappearance of all lesions in two consecutive observations not less than 4 wk apart	Disappearance of all lesions in two consecutive observations not less than 4 wk apart
PR	$\geq 50\%$ decrease in SPD of all index lesions compared with baseline in two observations at least 4 wk apart, in absence of new lesions or unequivocal progression of non-index lesions	$\geq 50\%$ decrease in tumor burden compared with baseline in two observations at least 4 wk apart
SD	50% decrease in SPD compared with baseline cannot be established nor 25% increase compared with nadir, in absence of new lesions or unequivocal progression of non-index lesions	50% decrease in tumor burden compared with baseline cannot be established nor 25% increase compared with nadir
PD	At least 25% increase in SPD compared with nadir and/or unequivocal progression of non-index lesions and/or appearance of new lesions (at any single time point)	At least 25% increase in tumor burden compared with nadir (at any single time point) in two consecutive observations at least 4 wk apart

Table 2. Derivation of irRC overall responses

Measurable response Index and new, measurable lesions (tumor burden),* %	Nonmeasurable response		Overall response Using irRC
	Non-index lesions	New, nonmeasurable lesions	
↓100	Absent	Absent	irCR [†]
↓100	Stable	Any	irPR [†]
↓100	Unequivocal progression	Any	irPR [†]
↓ ≥ 50	Absent/Stable	Any	irPR [†]

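### Neither document says which of the two scans dates progression for PFS, so the date can depend on whether the patient continues to a confirming scan

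*SAP*

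**What the plan says.** **What counts as progression.** SAP 3.2, Table 1 defines irPD as "At least 25% increase in tumor burden compared with nadir (at any single time point) in two consecutive observations at least 4 weeks apart". The footnote to SAP Table 2 also makes irPD conditional on a second, consecutive assessment. Protocol 7.5.1 has the same requirement: "Confirmation by a repeat, consecutive assessment no less than 4 weeks from the date first documented". None of these says which scan supplies the PFS date.

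**Who has the second scan.** Protocol 5.4 (Cycle 6+) asks for it at 4 weeks ± 3 days, "only for patients who elect to continue on therapy until confirmation of progression"; footnote j of the Study Calendar agrees. Protocol 7.5.1 differs. There, "confirmation of irPD by a second scan in the absence of rapid clinical deterioration is required", and the same bullet then leaves it to the investigator's discretion.

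**How PFS is dated.** SAP Table 3 has a row for "Progression documented between scheduled visits", dated "Next scheduled visit". The row does not mention confirming scans, and the SAP does not define a scheduled visit, which could be the 14-day infusion visit or the 8-weekly tumor assessment. No row covers a patient with one irPD scan and no second scan. That patient could fall under investigator-claimed clinical progression (event) or under discontinuation for toxicity or another reason (censored at the last adequate assessment).

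**Table references.** The PFS definition in SAP 3.2 and the censoring rule in SAP 7.2 both point to Table 1. The dating and censoring rules are in Table 3.

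**Scan schedule.** Footnote j says that "tumor measurements are to be repeated every 8 weeks (within 7 days prior to C9D1, C13D1, C17D1, etc". After a progression that is not confirmed, Protocol 5.4 has "radiographic tumor assessments every 8 weeks from Day 1 of the current treatment cycle until progression".

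**The concern.** Whether a patient goes on to a confirming scan is settled after randomization, by the patient and the investigator, and probably depends on how the patient feels. If the event date moves later only for those who continue, PFS partly measures that decision.

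Unequal continuation is plausible. The protocol expects MABp1 to relieve fatigue. Section 1.6 reports less fatigue, pain and appetite loss in the pilot, and section 1.5 regrets that some pilot patients who may have been benefiting were stopped at radiographic progression. Blinding does not remove a difference that works through symptoms. PFS is tested at two-sided 0.05 (SAP, Secondary Effectiveness Endpoints).

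**Working it through.** **1. Reproduce the plan's calendar.** With 14-day cycles, the day of CkD1 is (k − 1) × 14. C5D1 = 4 × 14 = day 56 (week 8), C9D1 = 8 × 14 = day 112 (week 16), C13D1 = 12 × 14 = day 168 (week 24). This matches the plan's week 8 assessment and 8-week steps.

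**2. Date one patient under each reading.** Growth is first seen at C5D1, day 56. The confirming scan falls on day 56 + 28 ± 3 = 81 to 87.

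| Reading | Event day |
|---|---|
| First growth scan | 56 |
| Confirming scan, actual date | 81–87 |
| Table 3 row, next 14-day visit | 84 (C7D1), or 98 (C8D1) if the scan falls after day 84 |
| Table 3 row, next 8-weekly tumor visit | 112 |
| Patient stops after the day-56 scan | 56, or censored |

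**3. Allow for the scan windows.** The windows are C5D1 ± 3 days, 0–7 days before C9D1 and C13D1, and ± 3 days for the confirming scan. Relative to the first growth scan, the event is dated later by 25–31 days (confirming scan), 25–44 days (next 14-day visit) or 53–63 days (next tumor visit). Examples of the extremes: 98 − 54 = 44, 112 − 59 = 53 and 168 − 105 = 63.

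**4. Effect on the test when the drug does nothing.** This is a log-rank simulation with 400 versus 200 patients (SAP 5), scans every 8 weeks, and identical growth and death in both arms. Assumed, not in the documents: median time to growth 1.5 or 2.5 months, and the continuation rates. Median time to death is set at the SAP's control figure, 4.6 months. Entries are two-sided rejection rates at 0.05 over the two growth medians, 1,500 runs each. Monte Carlo standard error is about √(0.05 × 0.95 / 1500) = 0.006.

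| Continuing, MABp1 / placebo | First scan | Next 14-day visit | Next 8-weekly visit | Unconfirmed censored |
|---|---|---|---|---|
| 50% / 50% | 0.053–0.055 | 0.053–0.057 | 0.052–0.053 | 0.045–0.048 |
| 55% / 45% | 0.055–0.056 | 0.058–0.075 | 0.065–0.104 | 0.062–0.067 |
| 60% / 40% | 0.047–0.050 | 0.088–0.139 | 0.131–0.227 | 0.117–0.142 |
| 70% / 40% | 0.051–0.056 | 0.121–0.243 | 0.230–0.443 | 0.181–0.182 |

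The last column dates continuing patients at the next 8-weekly visit and censors the others at their first irPD scan. At 50% / 50%, median PFS goes from 60–62 days (first scan) to 73–85 days (14-day reading) or 74–95 days (8-week reading), about equally in both arms.

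**5. One-sided results in favor of MABp1 at 0.025.** Here the assumed medians are 2.0 months to growth and 5.2 months to death, and unconfirmed irPD counts at the first scan. The ranges come from repeated runs of 2,000–4,000 replicates.

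| Continuing | 4-week shift | 8-week shift |
|---|---|---|
| 55% / 45% | 5–6% | 8% |
| 50% / 30% | 9–11% (HR 0.94) | 17–19% (HR 0.90) |

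With equal shares, or with first-scan dating, the rate is about 2.5–3%.

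**6. Direction.** Later dating for those who continue favors the arm with more continuing patients. Censoring unconfirmed progression works the other way, because it removes more events from the arm with fewer continuing patients. The two readings therefore push the hazard ratio in opposite directions.

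**The case against.** The strongest reply is that the between-visits row was never meant for confirming scans. Protocol 5.4 and footnote j treat progression as documented at the first scan and confirmed afterwards, and 7.5.1 counts the 4 weeks from first documentation. On that reading the row covers an off-schedule first scan, and growth seen at C5D1 or C9D1 is not shifted. The confirming scan is itself protocol-timed, and 4 weeks after C5D1 is C7D1, a scheduled infusion visit. The SAP also defers detailed evaluation methods to an Imaging Review Charter, not available here, which may address dating. Scans are read centrally by blinded radiologists and treatment is double-blind, which limits unequal continuation.

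Much of this stands. A reader might infer that Table 3 plainly moves every confirmed progression to a later visit; the text does not say so. A reader might also infer that a drug acting only on symptoms would appear to delay tumor growth. That needs unequal continuation, for which the documents give no figure. The text does not, however, settle the first scan as the date either, and the patient with a single irPD scan is left without a rule on any reading.

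Two further inferences should not be drawn. Tying scans to dosing cycles is not a material source of bias: assumed 2-week delays in 15–30% versus 5–10% of patients give a hazard ratio of only 0.98–0.99. The scan schedule after a refuted progression is largely a general rule (footnote j) with a specific exception (the procedures text). It needs clarifying but is not an outright contradiction.

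**Conclusion.** The point holds as a gap in the PFS definition. The same week-8 growth can be dated week 8, about week 12 (day 98, week 14, at the latest under the 14-day reading) or week 16 in a patient who continues, and week 8 or censored in one who stops. The calendar spread follows from the documents alone.

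The bias is conditional. With equal continuation by arm, the test keeps its level and only median PFS lengthens. With unequal continuation, one-sided 0.025 becomes about 5–8% at 55% versus 45%, and about 9–19% at 50% versus 30%. Those figures rest on assumed continuation rates and growth and death medians, and on Table 3 being applied to the confirming scan. PFS is secondary, and the primary overall survival analysis is unaffected. The change should be made, but the primary conclusion does not depend on it.

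**What to change.** In SAP 3.2 and Table 3, before unblinding:

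- State that confirmed irPD is dated at the first of the two qualifying scans, using the actual scan date, and that this overrides the between-visits row.
- Add a row that counts a single irPD scan with no confirming scan (the patient stops or dies) as progression at that scan. Censor these patients in a sensitivity analysis only; that analysis is itself distorted if continuation differs by arm, in the opposite direction (step 6).
- Define the scheduled visit as the 8-weekly tumor assessment wherever the term remains; the clinical-progression row also uses it.
- Correct the references in SAP 3.2 and 7.2 from Table 1 to Table 3 where the dating and censoring rules are meant.

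In the protocol, reconcile 5.4, footnote j and 7.5.1 on who has a confirming scan, and 5.4 and footnote j on the schedule after a refuted progression.

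The SAP changes cost only wording and programming. Reconciling the schedule may add scans, depending on the choice. After growth at week 8 that is refuted at week 12, the procedures text gives week 12 + 8 = week 20, whereas the routine calendar gives weeks 16 and 24.
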